#### **8.4 METHOD OF ASSIGNING PATIENTS TO TREATMENT GROUP**

The randomized treatment kit number list is generated centrally by Sanofi. The IMPs are packaged in accordance with this list.

Patients will be randomized to receive either sotagliflozin 400 mg, sotagliflozin 200 mg, or placebo once daily during the randomized double-blind Treatment Period. Randomization (ratio 1:1:1) will be stratified by HbA1c at Screening ( $\leq 8.5\%$  and  $> 8.5\%$ ) and SBP at Screening ( $< 130$  mmHg,  $\geq 130$  mmHg).

The randomization and the treatment package allocation are performed centrally by an IRT. At the Screening Visit the Investigator or designee has to contact the IRT to receive the patient number.

  
At Visit 2 (Run-in), the IRT will be contacted for dispensing single-blinded placebo Run-in kit. At Visit 3 (Baseline), patient eligibility will be reviewed, the IRT will be contacted and corresponding treatment packages will be allocated.

After Visit 3 (Baseline), the IRT is contacted again each time new treatment package(s) allocation is required by the protocol. For each randomized patient, the IRT will allocate treatment package number(s) corresponding to the treatment group assigned. Treatment packages are allocated by the IRT using their treatment kit numbers.

A randomized patient is defined as a patient who is registered and assigned with a treatment kit number from the IRT, as documented in IRT.

A patient may not be enrolled in this study more than once (ie, enter Run-in or being randomized twice). In cases where original screen failure was due to reasons expected to change at rescreening and based upon the Investigator's clinical judgment, the patient can be rescreened prior to entering Run-in once for this study. In these cases, a patient will need to sign a new ICF, be registered as a rescreened in IRT, and assigned a new patient number in IRT (first Screening Visit is to be registered as screen failure in IRT), and complete again the Screening Visit procedures/assessments again.

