#### **10.4.1.4 Events of special Interest**

An EOSI is a serious or nonserious AE of scientific and medical concern specific to the Sponsor’s product or program, for which ongoing monitoring may be appropriate. Such events may require further investigation in order to characterize and understand them. These events should be reported on the specific e-CRF page (where applicable) and will only qualify for expedited reporting when serious (fulfilling SAE criteria).

The EOSIs for this study are:

- MACE (CV death, MI, or stroke) and other specific CV events (eg, heart failure leading to hospitalization)
- Severe hypoglycemia (see [Section 10.6.1](#))
- Genital mycotic infections (to include vulvovaginal candidiasis in females and candidal balanitis in males)
- Urinary tract infections
- Clinically relevant volume depletion and events related/possibly related to volume depletion
- Diarrhea
- Pancreatitis
- Bone fractures
- Venous thrombotic events, to include deep venous thrombosis and thromboembolism (to include pulmonary embolism)
- Diabetic ketoacidosis
- Renal events, to include 50% decline in eGFR, end stage kidney disease, renal death
- Malignancies of special interest (breast, bladder, renal cell, Leydig cell, pancreatic, prostate, and thyroid cancer)
- Adverse events leading to amputation.

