#### **All adverse events**

Adverse event incidence tables will present by system organ class (SOC) (sorted by internationally agreed order), high level group term (HLGT), high level term (HLT) and preferred term (PT) sorted in alphabetical order for each treatment group, the number (N) and percentage (%) of patients experiencing an AE. Multiple occurrences of the same event in the same patient will be counted only once in the tables within a treatment phase. The denominator for computation of percentages is the safety population within each treatment group.

Summaries of all TEAEs in each treatment group will include:

- The overview of AEs, summarizing number (%) of patients with any
  - Treatment-emergent AE
  - Serious TEAE
  - Treatment-emergent AE leading to death
  - Treatment-emergent AE leading to permanent treatment discontinuation.

- The number (N) and percentage (%) of patients with at least one TEAE by primary SOC, HLGT, HLT, and PT
- Summary of TEAEs by maximal severity (severe, moderate, mild), presented by primary SOC and PT
- Summary of TEAEs possibly related to IMP, presented by primary SOC, HLGT, HLT, and PT.

A detailed listing of TEAE summaries will be provided in the SAP.

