Chronic dialysis	(3) For dialysis, (3a) dialysis lasted for ≥ 90 days (e.g. end date – start date + 1 ≥ 90) as recorded in eCRF "Renal Event – Dialysis", OR (3b) positively adjudicated by CEC: Yes to the question ". Does the subject meet the criteria for ESRD".
Renal transplant	(4) "Renal transplant" captured in eCRF "Other procedure form", where adjudication is not required. PTs of Renal transplant (10038533), Renal and pancreas transplant (10052278), Renal and liver transplant (10052279) based on MedDRA v22.0.
Renal death	(5) Renal death as positively adjudicated by CEC: "Death - Non-Cardiovascular (Renal)" as the primary cause of death

EOSI not adjudicated*

Severe hypoglycemia	algorithm specified in Section 2.1.4.1 based on eCRF "Hypoglycemic Events"
Genital mycotic infections	PTs in Appendix C
Urinary tract infections	PTs in Appendix C,

AE Grouping	Criteria
Clinically relevant volume depletion and events related/possibly related to volume depletion	PTs in Appendix C
Diarrhea	Narrow search on “Noninfectious diarrhoea (SMQ)” [20000218] plus the following PTs (MedDRA v22.0): Gastroenteritis (10017888), Antidiarrhoeal supportive care (10055660), Enteritis (10014866), Enteritis leukopenic (10014877), Enterocolitis (10014893), Enterocolitis haemorrhagic (10014896)
Pancreatitis	PTs in Appendix C
Venous thrombotic events	PTs in Appendix C
Malignancies of special interest	Breast cancer: Narrow search on “Breast neoplasms, malignant and unspecified (SMQ)” [20000149] Prostate cancer: Narrow search on “Prostate neoplasms, malignant and unspecified (SMQ)” [20000152] Leydig-cell cancer: PTs of Leydig cell tumour of the testis (10024407) and Ovarian Sertoli-Leydig cell tumour (10073270) based on MedDRA v22.0 Thyroid cancer: PTs in Appendix C Renal cell cancer: PTs in Appendix C Pancreatic cancer: PTs in Appendix C Bladder cancer: PTs in Appendix C

EOSI AE leading to an amputation

Adverse event leading to an amputation	“AE Correction” as the reason for amputation in eCRF “Other Procedures related to Amputation”
AE potentially leading to an amputation *	PTs in Appendix C

* Search terms will be updated using the MedDRA version currently in effect at Sanofi at the time of database lock for EOSI identified by them. AE potentially leading to amputation: not one of EOSI defined in protocol, included and analyzed due to their relevance in regards to lower limb complications and amputations as a requirement from health authorities.

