2.3.2 Safety population

Safety analyses will be based on the safety population, defined as all randomized patients who receive at least one dose of double-blind IMP (regardless of the amount of treatment administered), analyzed according to the treatment actually received.

In addition:

- Nonrandomized but treated patients will not be part of the safety population; however, their safety data will be presented separately
- Randomized patients for whom it is unclear whether they took the IMP will be included in the safety population as randomized
- When a patient is exposed to both sotagliflozin and placebo, the patient will be analyzed in the appropriate sotagliflozin group (depending on the treatment kits taken [400 mg or 200 mg])
- When a patient is exposed to both sotagliflozin 400 mg (treatment kits) and 200 mg (treatment kits), the patient will be analyzed in the sotagliflozin 200 mg group
- Randomized patients will be excluded from the safety population only if there is documented evidence (ie, all study dates recorded as no medication taken) that patients have not taken the study treatment. If a patient is dispensed double-blind IMP and is lost to follow-up without any documented evidence, the patient will be considered exposed.

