- For quantitative safety parameters based on central laboratory/reading measurements, descriptive statistics will be used to summarize results and change from baseline values by visit and treatment group for the 52-week entire treatment period only. Summaries will include the last on-treatment value. The last on-treatment value is commonly defined as the value collected at the same day/time of the last administration of IMP for the 52-week entire treatment period. If this value is missing, this last on-treatment value will be the closest value prior to the last administration of IMP during the 52-week entire treatment period.
- The analysis of the safety variables will be essentially descriptive and no systematic testing is planned. Relative risks versus placebo and their 95% CIs may be provided, if relevant.
- Selected safety analyses will be summarized by age, gender, racial subgroups, and other pertinent subgroups (see details in [Section 2.4.5.1](#) and [Section 2.5.2](#)).

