- All treatment-emergent adverse event by primary SOC, HLG, HLT, and PT, showing number (%) of patients with at least 1 treatment-emergent adverse event sorted by the SOC internationally agreed order. The other levels (HLG, HLT, PT) will be presented in alphabetical order
- Number (%) of patients experiencing TEAE(s) presented by PT, sorted by decreasing incidence of PT in the sotagliflozin 400 mg group
- All treatment-emergent adverse events by primary SOC and PT, showing the number (%) of patients with at least 1 treatment-emergent adverse event, sorted by the internationally agreed SOC order and by decreasing incidence of PTs within each SOC in the sotagliflozin 400 mg group. This sorting order will be applied to all other similar tables, unless otherwise specified
- All treatment-emergent adverse events regardless of relationship and related IMP by primary SOC, HLG, HLT and PT, showing the number (%) of patients with at least 1 treatment-emergent adverse event, sorted by the internationally agreed SOC order. The other levels (HLG, HLT, PT) will be presented in alphabetical order
- All treatment-emergent adverse events by maximal severity, presented by primary SOC and PT, showing the number (%) of patients with at least 1 treatment-emergent adverse event by severity (ie, mild, moderate, or severe), sorted by the sorting order defined above
- Common TEAEs (PTs with incidence $\geq 2\%$ in any treatment group) by primary SOC, HLG, HLT, and PT, sorted by internationally agreed order of SOCs. The other levels (HLG, HLT, PT) will be presented in alphabetic order.
- Common TEAEs (PTs with an incidence $\geq 2\%$ in any treatment group) will be provided as appropriate by primary SOC, and PT and by demographic factors including gender (Male, Female), age group (<50, ≥ 50 to <65, ≥ 65 years of age), race (White, Black or African American, Asian, other), baseline SBP category (<130 mmHg, ≥ 130 mmHg), and prior antidiabetic medication (no antidiabetic therapy, insulin, non-insulin). SOC will be sorted by internationally agreed order and the PT by decreasing incidence within each SOC in the sotagliflozin 400 mg group, as described above.
- TEAEs (PTs with incidence $\geq 5\%$ in any treatment group) by primary SOC, HLG, HLT, and PT, sorted by internationally agreed order of SOCs. The other levels (HLG, HLT, PT) will be presented in alphabetic order.

- Acute renal failure (narrow search on “Acute renal failure (SMQ)” [20000003]) by PT.

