The following renal events will be listed along with the adjudication outcome if applicable, including events,

- i. recorded in eCRF “GFR decrease”,
- ii. recorded in eCRF “Renal Event – Dialysis”,
- iii. identified as “Renal transplant” in eCRF “Other procedure”,

Renal death will be part of all deaths specified above.

Other EOSIs

For EOSIs that are not adjudicated, the number (%) of patients with at least one event will be summarized by treatment group and by PT (as identified in Table 3 in Section 2.1.4.2).

Severe hypoglycemia will be included in the summary of hypoglycemia (See Section 2.4.5.1).

AE leading to an amputation is described in the section below.

Analysis of Amputation

The number (%) of patients with amputation will be summarized by treatment group and by PT and LLT during the study (ie, regardless of on- or post-treatment). Amputation is a procedure recorded in eCRF “Other Procedures related to Amputation”. Patients who had a procedure related to amputation will be listed.

The number (%) of patients with an “AE leading to an amputation” will be summarized by treatment group and by PT (as identified in Table 3 in Section 2.1.4.2; these PTs in Table 3 were requested by the European Medicines Agency(EMA)/ Pharmacovigilance Risk Assessment Committee (PRAC) Assessment Report, 09 February 2017). The associated list will be provided as well, with patients who had an amputation procedure flagged. “AE potentially leading to an amputation” represents the condition that may potentially lead to the amputation procedure, but not in all cases an amputation has occurred.

Analysis of pretreatment and posttreatment adverse events

- All pretreatment adverse events by primary SOC and PT, showing the number (%) of patients with at least 1 pretreatment adverse event, sorted by the internationally agreed SOC order and decreasing incidence of PTs within each SOC in the sotagliflozin 400 mg group
- All posttreatment adverse events by primary SOC and PT, showing the number (%) of patients with at least 1 posttreatment adverse event, sorted by the internationally agreed SOC order and decreasing incidence of PTs within each SOC in the sotagliflozin 400 mg group

Listings

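### Single-sex adverse event terms and prostate cancer are divided by patients of both sexes in the main AE and EOSI tables, which understates incidence in the patients who can have them

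*Protocol*

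**What the plan says.** Protocol 11.4.3.1 (All adverse events) and SAP 2.4.5.2 (Generalities) carry the same sentence: "The denominator for computation of percentages is the safety population within each treatment group". SAP 2.3.2 gives that population as "defined as all randomized patients who receive at least one dose of double-blind IMP", so it contains both sexes.

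Single-sex terms are among the pre-specified events of special interest (EOSIs). Protocol 10.4.1.4 lists "Genital mycotic infections (to include vulvovaginal candidiasis in females and candidal balanitis in males". SAP Table 3 defines a separate malignancy group that begins "Prostate cancer: Narrow search on". Neither is adjudicated, and for such events SAP 2.4.5.2 states: "For EOSIs that are not adjudicated, the number (%) of patients with at least one event will be summarized by treatment group and by PT". No split by sex is given there.

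Two provisions do bring in sex. For preferred terms (PTs) that reach 2% in any arm, SAP 2.4.5.2 says that tables "will be provided as appropriate by primary SOC, and PT and by demographic factors including gender (Male, Female", with other factors following. SAP 2.4.5 adds: "Selected safety analyses will be summarized by age, gender, racial subgroups, and other pertinent subgroups". That sentence points to Sections 2.4.5.1 (hypoglycemia) and 2.5.2 (handling of secondary efficacy variables), and neither deals with single-sex events.

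**The concern.** Protocol 4.5 says that the drug class has been associated with more genital infections and names genital mycotic infection, in males and females, among the programme's identified and potential risks. Its incidence is therefore a safety figure that readers will look up. All safety summaries are descriptive, so the printed percentage is itself the result.

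When men stand in the denominator for vulvovaginal candidiasis, or women in the denominator for balanitis or prostate cancer, the percentage is not the risk in the patients who can have the event. It also depends on the sex mix of the arm. Sex is not a stratification factor: Protocol 8.4 states "Randomization (ratio 1:1:1) will be stratified by HbA1c at Screening", and the only other factor is systolic blood pressure.

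**Working it through.** **Inputs.** The planned arm size is 92 (Protocol 11.1), and I assume that nearly all are dosed. The documents give neither a sex split nor an expected incidence, so the share f of the sex at risk is an assumption, shown from 30% to 60%.

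**The plan's own figure.** With a difference of 0.5, an SD of 1.2 and two-sided alpha of 0.05, the normal approximation gives 2 × 1.2² × (1.960 + 0.842)² / 0.5² = 90.4, or 91 per arm for 80% power. At 92 per arm, power is 80.7% (80.3% by the noncentral t). The stated 92 is reproduced. It serves here only as the arm size.

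**Which items are affected.** Of the eight genital mycotic infection PTs in Appendix C, five are single-sex: vulvovaginal candidiasis, vulvovaginal mycotic infection, candida cervicitis, balanitis candida and fungal balanitis. The other three (genital candidiasis, genital infection fungal, urogenital infection fungal) can occur in either sex. Among the malignancy groups, prostate cancer is single-sex as a category. The Leydig-cell group pairs a testicular term with an ovarian one, so as a category it spans both sexes.

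**Dilution.** With x cases, the plan shows x/92. The incidence in the sex at risk is x/(92f). The ratio is 1/f. For x = 4 the plan shows 4/92 = 4.3%:

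| f (assumed) | Patients of that sex | 4 cases in that sex | Factor |
|---|---|---|---|
| 30% | 28 | 14.3% | 3.3 |
| 40% | 37 | 10.8% | 2.5 |
| 50% | 46 | 8.7% | 2.0 |
| 60% | 55 | 7.3% | 1.7 |

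**Reach of the by-gender table.** Since 1/92 = 1.1% and 2/92 = 2.2%, a term enters only if at least two patients in some arm share the same PT. Suppose that three women in one arm have the three different female PTs, and no arm has two cases of any one of them. Each PT then shows 1.1% and none enters, yet three cases are 3/46 = 6.5% to 3/28 = 10.7% of the women for f of 50% to 30%. A single prostate cancer would appear only as 1.1%; with half the arm men it is 1/46 = 2.2% of them. The SAP does not state the denominator of the by-gender table, and the general rule, read literally, would still apply to it.

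**Comparison between arms.** If f is the same in both arms, it cancels from the ratio, and the risk difference is multiplied by f. The SD of the chance difference in f is √(2f(1−f)/92), which is 7.2 points at f = 40%. The 95% range is about ±14 points. At equal risk in women, arms with 50% and 40% women would show an apparent ratio of 0.50/0.40 = 1.25.

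**The case against.** The strongest reply is that little is lost.

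- The rule is clear and identical in both documents, and the percentage is a well-defined proportion of treated patients. It is not presented as a sex-specific risk.
- The by-gender table will catch most terms that matter. With a true 10% risk in 28 to 46 women, 2.8 to 4.6 cases are expected, and the chance of at least two in a single arm is about 78% to 95%. It is higher over several arms at similar risk.
- Counts are printed beside percentages, gender is tabulated by arm, and the AE listings carry gender, so a reader can recover the sex-specific rate closely.
- Chance imbalance is small beside sampling noise. With 40% women and 10% risk, 92 × 0.40 × 0.10 = 3.7 cases are expected. A one-SD imbalance shifts this by 7.2/40 = 18%, or about 0.7 of a case, against a 95% sampling range of roughly ±1.96 × √3.7 ≈ ±3.8 cases.

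Most of this stands and limits the weight of the point. It does not remove it. The by-gender table is conditional, works PT by PT, and has no stated denominator. That a reader could rebuild the rate from other tables is no reason to print a diluted one for a pre-specified risk.

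**Conclusion.** The point holds for single-sex PTs and for the prostate cancer EOSI, in the main AE tables and the EOSI-by-PT tables. There, incidence in the patients at risk is understated by 1/f, about 1.7- to 3.3-fold for f of 60% to 30%. The range rests wholly on that assumed split.

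A reader might infer three stronger things that the documents do not support.

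- **That all adverse event percentages are affected.** They are not: most terms can occur in either sex, and the SAP plans a by-gender table for terms that reach 2% in any arm.
- **That the headline genital mycotic infection figure is wrong.** The combined EOSI covers women and men, so the full safety population is its proper denominator. What is missing is the split by sex.
- **That the comparison between arms is biased.** The ratio is unaffected unless the sex mix happens to differ, and no significance test is planned on safety data.

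This is a modest reporting improvement. No efficacy conclusion is touched.

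**What to change.** In SAP 2.4.5.2, as an exception to the general denominator rule:

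1. For PTs that can occur in one sex only, and for the prostate cancer EOSI, use the number of safety patients of that sex in the arm as the denominator, and footnote the tables. List these PTs in the SAP so that the choice is fixed in advance of programming.
2. Show the genital mycotic infection EOSI for women, for men and overall. The overall row keeps the full safety population.
3. State that the by-gender table uses the safety patients of each sex in the arm as its denominators.

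Keep the 2% and 5% inclusion cut-offs on the full safety population. If they were applied to sex-specific percentages, one case in 28 to 46 women (3.6% to 2.2%) would pass the 2% cut-off, and the word common would have two meanings in one table.

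The cost is SAP wording, table shells and a few extra rows. Gender is already collected. The downside is less stable percentages from smaller denominators, so counts should stay beside them. SAP 1.6 records that the first-step analysis has already been run, so the change should be dated and labelled as a descriptive addition.

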### **Death and serious adverse events**

Death and treatment-emergent SAEs will be summarized and presented as number and percent of patients in each treatment group.

The following deaths summaries will be generated:

- Number (%) of patients who died by study period (on-study, on-treatment, post-study) summarized on the safety population by treatment received
- Death in non-randomized patients or randomized and not treated patients
- Treatment-emergent AE leading to death (death as an outcome on the AE e-CRF page as reported by the Investigator) by primary SOC, HLGT, HLT, and PT showing number (%) of patients sorted by internationally agreed order of SOC and alphabetic order of HLGT, HLT, and PT

### **Adverse events leading to permanent treatment discontinuation**

Treatment-emergent AEs leading to permanent treatment discontinuation will be summarized and presented as number and percent of patients in each treatment group.

#### **11.4.3.2 Analyses of hypoglycemia**

The number (%) of patients and rate in patient years (2 types: the number of patients with events or the total number of events per 100 patient year) of all hypoglycemia events reported by the patient and confirmed by the Investigator, severe, and/or documented symptomatic hypoglycemia, will be summarized by treatment group respectively. Their pattern of occurrence over time will also be assessed, as appropriate.

#### **11.4.3.3 Analyses of adverse events of special interest**

Pregnancy and overdose will be included in overall AE summaries if any are reported. An ALT increase >3 times ULN is included in laboratory PCSA summary if any.

